
Based on our preliminary data about 25%-50% of the participants may fail to achieve abstinence/maintain abstinence after their quit date, using only the behavioral counseling provided. Our preliminary studies are not yet complete and our abstinence rates have ranged been as high as 75% at other times when we have undertaken interim analysis. To enhance abstinence rates in the present study, we have both increased the counseling frequency, in comparison to our previous study, and provided a monetary bonus for abstinence. With these adjustments, we feel it is reasonable to expect 60%-75% of those in the placebo group (counseling alone) will be abstinent at the 28-day post-quit assessment. Based on the initial clinical trials with both drugs, we expect 75%-80% of those in both drug groups to have achieved abstinence by day 28 post-quit. Our power calculations for interactions involving abstinence status, treatment and genotype have

taken this range of abstinence into account (see page 29). We have also outlined a strategy for comparing all participants in the drug treatment groups to placebo, similar to those we conducted between the Quit and Control groups in our preliminary studies. This approach is outlined in our data analysis section, along with our plan to evaluate differences in abstinence status between and within groups.

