We estimated power based on 354 subjects and a Type I error rate of 0.05. Power calculations were repeated for each of the three models. For Hypothesis 1, we estimated power for the group contrast between placebo and either bupropion or nortriptyline. A sample size of 354 subjects provides 80% power to detect effect sizes of .17, .32 and .30 standard deviations between these groups for Models 1, 2 and 3, respectively. Given the variability estimates in the raw startle magnitude scores we found by applying the three models to our previous work, these effect sizes translate into group differences in startle magnitude of 4, 22 and 16

µvolts, for Models 1,2 and 3, respectively. These values are well within the range observed in our preliminary studies where the overall difference between treatment and controls averaged 27 µvolts. This range also provides adequate power for detecting interactions with valence for any of the Models, as the range of differences between positive and negative valence between groups, is above 16 µvolts. For Hypothesis 2, we estimated power for the genotype comparisons across a range of possible prevalence for the “at risk” allele, among smokers. The expected allele frequency among smokers is shown in **Table 3**. Data from controls are provided for comparison but except in the case of the NET, are not considered in the power calculations. Power analyses for genotype effects are summarized in **Table 4**. Effect sizes are shown in standard deviation units. The corresponding difference in raw scores (µvolts) is shown in parentheses. Our major hypothesis involving genotype center on the DRD2, for which the A1 is the “at risk allele. As shown in **Table 3**, the expected frequency in our sample of smokers is above 40%. Effect sizes at this frequency and above vary from .15-.30, which corresponds to differences of 3-16 µvolts (see **Table 4**), for the three respective models. In our preliminary studies, the average difference in startle magnitude across all valences between A1 and A2 smokers who quit during the study was 26 µvolts, so we will have adequate power for these comparisons.

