As described in the proposal, we will also examine other genotypes in exploratory analysis. For purposes of these comparisons, the “at risk” allele can be considered the GG allele of the NET, the L form of the DRD4 and the SERT, and the DAT 10/10. Data on the GG genotype of the NET are unknown for smokers so we used the control data from Zill. For all but the DRD4 the effect sizes and corresponding startle magnitudes are similar to the A1. For the DRD4 L allele the frequency is estimated at .24, corresponding to an effect size of .2-.35, and startle differences between 4-25 µvolts, across the three models. If the differences in startle magnitude are similar to those of the A1, we will still have adequate power to detect them, although this might be at the upper range for Model 2.

For the moderation of emotional reactivity during cessation by genotype, we again provide estimated power for the three models in **Table 5**. The effect estimates represent the difference in emotional reactivity

Prevalence of “at risk” allele	Model 1	Model 2	Model 3
.5	.32 (7)	.57 (39)	.57 (31)
.4	.34 (7)	.60 (41)	.59 (32)
.3	.37 (8)	.63 (43)	.62 (34)
.2	.42 (9)	.72 (49)	.70 (39)

between placebo and bupropion or nortriptyline between each of the two genotypes (e.g. A1 vs. A2). Our preliminary studies indicate that the difference between A1 participants in Quit group and A1 Controls (adjusting for baseline) ranged from 25-60µvolts over the two week of cessation period. Corresponding differences for A2s ranged from 25-2µvolts, and a significant interaction between genotype and Group (Quit vs. Control) was observed (i.e., A1 Quitters showed an elevated startle during cessation. Based on this estimate we will have

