adequate power for detecting 2 way interactions with genotype, for all Models for our primary hypothesis (DRD2), and for our exploratory analysis of other genotypes, if similar results are observed. Our analytic strategy also calls for exploratory analysis of possible interactions between genotype abstinence status (Abstainers Relapsers Never Quitters), and treatment conditions. We expect all smokers in treatment to experience significant startle elevation as a consequence of abstinence or the reduced smoking observed among the Relapsers or Never Quitters, at least through the first week following cessation. If we estimate an overall abstinence rate at the end of treatment of 60%, and an at risk allele frequency of .43 (for the A1), that is the equivalent of a .26 “at risk” allele rate in **Table 5**. Therefore we should be able to detect differences in startle magnitude of 8-43µvolts, depending on the Model, for interactions between genotype, abstinence status and treatment. This range of startle activity also provides us with adequate power to detect interactions with valence, should they occur, as seen in our previous studies. Differences between A1 Relapsers, Never Quitters and Abstainers and A1 Controls across valences ranged from 7 to 40µvolts, across assessments. For A2s the range was more narrow (4-22µvolts). Thus, we should have we should have adequate power to detect interactions with valence, genotype, abstinence and treatment, should they occur.

Power for hypothesis 3 was estimated by dichotomizing emotional reactivity into two groups (high versus low), in order to make use of available standard power formulas. Our actual dependent measure will be a continuous measure of startle, which will offer a much finer gradation of the incremental differences in

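### The 8-43 µV quoted as detectable for genotype x abstinence x treatment comes from a two-way table; the three-way threshold is about 1.9 to 2.2 times larger

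*Combined protocol and SAP*

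**What the plan says.** The Power section introduces the analysis in these words: "Our analytic strategy also calls for exploratory analysis of possible interactions between genotype abstinence status (Abstainers Relapsers Never Quitters), and treatment conditions". The detectable difference is then derived in one step. It starts "If we estimate an overall abstinence rate at the end of treatment of 60%, and an at risk allele frequency of .43 (for the A1"), and continues "that is the equivalent of a .26" at-risk rate in Table 5. From this it reports 8-43 µV, "depending on the Model, for interactions between genotype, abstinence status and treatment". The values 8 and 43 are the Model 1 and Model 2 entries in the .3 row of Table 5; the Model 3 entry is 34.

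The same section defines the effects in Table 5 as the difference in reactivity "between placebo and bupropion or nortriptyline between each of the two genotypes". The basis for all the calculations is given as: "We estimated power based on 354 subjects and a Type I error rate of 0.05".

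The section on abstinence compliance and startle assessments expects "60%-75% of those in the placebo group (counseling alone) will be abstinent at the 28-day post-quit assessment", and for the drugs "we expect 75%-80% of those in both drug groups to have achieved abstinence by day 28 post-quit". It adds that the power calculations for interactions of abstinence, treatment and genotype allowed for this range. The Power section shows only the 60% case.

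**The concern.** The product .43 x .60 = .258 is correct, but it is the share of the sample that is both A1 and abstinent. Treating it as a prevalence puts A1 non-abstainers in the same group as all A2 participants. Table 5 then answers whether the drug effect differs between A1 abstainers and everyone else. The named interaction asks something else: whether the genotype difference in drug effect itself differs between abstainers and non-abstainers. That is a difference between two Table 5 contrasts, each estimated on part of the sample, so its standard error must be larger.

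The pilot ranges do not fill the gap. The 7-40 µV (A1) and 4-22 µV (A2) ranges are simple differences from Controls who went on smoking. So is the 25-60 µV range, which the plan cites for the two-way claim. None is a three-way contrast, so none shows whether any Model is adequately powered.

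At stake is how a null result is read. If the plan says 8-43 µV is detectable, a null finding may be taken as evidence that abstinence does not change the genotype-by-drug effect, when the study had little chance of showing it.

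**Working it through.** **Inputs from the Power section.** N = 354; alpha .05; 80% power; A1 frequency p = .43; abstinence a = .60; Table 5 .3 row = .37/.63/.62 SD (8/43/34 µV) for Models 1/2/3; correlations between and within sessions of .03/.45, .7/.9 and .6/.9. Abstinence of 60-75% (placebo) and 75-80% (drug) is from the abstinence section.

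**Assumptions.** Two-sided test; equal allocation, 354/3 = 118 per arm; placebo against one drug arm; abstinence scored yes/no and independent of genotype; responses averaged over valence.

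**1. The plan's figure.** .43 x .60 = .258, rounded to .26. The .3 row gives 8/43/34 µV, so 8-43 is traced exactly. Linear interpolation to .26 (.6 x the .3 row + .4 x the .2 row) would give 8.4/45/36 µV.

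**2. Variance factors.**
- Two-way: 1/[q(1-q)] = 1/(.3 x .7) = 4.76 for the .3 row.
- Three-way: 1/[p(1-p)a(1-a)], averaged over the two arms. At 60% in both: 1/(.43 x .57 x .6 x .4) = 17.0.

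The ratio of detectable differences is the square root of the ratio of these factors. SD, correlations and z-values cancel.

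| Placebo / drug abstinence | Three-way factor | Ratio to .3 row | Power at printed values |
|---|---|---|---|
| 60% / 60% | 17.0 | 1.89 | 32% |
| 60% / 75% | 19.4 | 2.02 | 28% |
| 60% / 80% | 21.25 | 2.11 | 26% |
| 75% / 75% | 21.8 | 2.14 | 26% |
| 75% / 80% | 23.6 | 2.23 | 24% |

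Power = Φ(2.80/ratio - 1.96); for example Φ(2.80/1.89 - 1.96) = .32. Pooling the two drug arms changes the ratios little: 1.89 (60/60), 1.98 (60/75), 2.20 (75/80). No common abstinence rate rescues the figure: a(1-a) is largest at 50%, where the ratio is still 1.85.

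**3. Thresholds in µV.** Table 5 implies mean SDs of 21.4/68.3/54.8 µV. Scaling the .3 row:
- 60/60: .37 x 1.89 x 21.4 = 15; .63 x 1.89 x 68.3 = 81; .62 x 1.89 x 54.8 = 64.
- 75/80: 18, 96 and 76.

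Scaling all four rows gives 14-15 / 80-83 / 63-65 µV at 60%, and 15-18 / 86-98 / 68-77 µV over the expected rates.

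**4. Cross-check from Table 5 alone.** Interpolating to .43 gives .334/.591/.584 SD. Comparing that contrast between 60% abstainers and 40% non-abstainers multiplies its standard error by 1/√(.6 x .4) = 2.04, giving .68/1.21/1.19 SD, or about 15/82/65 µV.

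**5. Direct calculation from the stated correlations.** The SD of a participant's mean is √[(1 + 2 x .45 + 9 x .03)/12] = .425 for Model 1 (3 valences x 4 sessions), √[(1 + 3 x .9 + 12 x .7)/16] = .870 for Model 2 (4 x 4) and √[(1 + 3 x .9 + 8 x .6)/12] = .842 for Model 3 (4 x 3). Simulation with these SDs (5000 runs, 118 against 118) gave power at the printed values of 34/26/27% at 60/60 and 25/20/21% at 75/80. The thresholds were 14/91/70 and 17/109/84 µV.

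This route does not reproduce Table 5 exactly. For the two-way .3 row the closed form gives .338/.692/.670 SD against the printed .37/.63/.62.

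**6. Cell sizes.** A1 non-abstainers per arm = 118 x .43 x (1-a): 20.3, 12.7 and 10.1 at a = .60, .75 and .80.

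**The case against.** The strongest reply accepts the 1.89 and disputes the rest.

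- **The µV figures are less certain than they look.** This stands. The table-scaled ranges reflect only spread across Table 5 rows. The direct route puts Models 2 and 3 some 10-13% higher and Model 1 about 6-7% lower, and the SAS settings are not given. The ratio is unaffected.
- **The upper multipliers use day-28 rates, whereas the 60% is labelled end of treatment.** Partly stands. The end-of-treatment rates the plan cites for Hypothesis 3 (42% placebo, 64% nortriptyline) give √(17.23/4.76) = 1.90. But day 28 is the last startle session, and the abstinence section says its range was used in the power calculations.
- **60% is the cautious end for the plan's own look-up.** True: .43 x .80 = .34 would give a smaller Table 5 threshold. For a real three-way contrast it is the favourable end of the expected range, because higher abstinence shrinks the non-abstainer cells.
- **Rounding .26 to the .3 row explains part of the gap.** Against an interpolated .26 the multiplier is 1.81 to 2.13, so most of it remains.
- **The plan names three abstinence levels, not two.** Correct, and it works against the printed figure. Abstainers against one non-abstinent subgroup holding an assumed 24% to 16% of the sample gives about 2.2 to 2.6.
- **The pilot found a significant Valence x Time x Abstinence x Genotype interaction.** It did, with 62 genotyped participants. That contrast involves valence and time, and compares quitters with Controls rather than drug with placebo, so it does not support 8-43 µV.
- **The analysis is exploratory.** True. This limits the consequence but does not make the figure correct.

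**Conclusion.** The concern holds. The printed 8-43 µV is the threshold for a two-way contrast and is too small for the interaction named. The error is in the choice of contrast, not in the multiplication.

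For a yes/no, valence-averaged three-way contrast the threshold is 1.89 times the printed row at 60% abstinence and 2.02-2.23 times at the protocol's expected rates. Power at the printed values is 32% and 24-28% respectively on the Table 5 scale, and 34% down to 20% by direct simulation. The ratio rests on abstinence being independent of genotype and, where arms differ in abstinence, on equal allocation. The absolute µV values are approximate.

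Claims about interactions with valence have a different error variance and are not refuted here. Sample size and the primary hypotheses are unaffected.

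**What to change.** In the Power section, state that Table 5 covers two-way contrasts only, and replace the 8-43 µV sentence with text such as:

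> For the valence-averaged treatment x genotype x abstinence (yes/no) contrast at A1 frequency .43, the difference detectable with 80% power, scaled from Table 5, is about 14-15, 80-83 and 63-65 µvolts (Models 1, 2, 3) if 60% are abstinent in every arm, and about 15-18, 86-98 and 68-77 µvolts if 60-75% of placebo and 75-80% of drug participants are abstinent. This analysis is exploratory and will be reported as estimates with 95% CIs.

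Preferably take the figures from a PROC MIXED re-simulation over those abstinence rates, with relapsers and never quitters both combined and separate, as the protocol plans to analyse them. Until that is run, treat the µV values as provisional.

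Do not call this interaction adequately powered under any Model unless a like-for-like three-way estimate supports it. The .26 look-up may stay only if relabelled as A1 abstainers versus all others, by treatment. Derive power for interactions with valence separately, from a stated correlation assumption.

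The cost is a change to the power text, or one extra simulation with the existing code. A stated figure becomes less favourable; design, sample size and primary hypotheses do not change.

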### Primary Hypotheses

1. The emotional reactivity of smokers during nicotine withdrawal will be significantly higher among those that receive placebo vs. either bupropion or nortriptyline therapy for smoking cessation. Emotional reactivity will be assessed using the eye blink response to an acoustic startle probe and by evaluating responses to emotionally valent stimuli (positive, negative, cigarette) relative to neutral visual slides.
  - 1.1. Mixed model repeated measure regression analyses will be used to evaluate this hypothesis, regressing peak startle magnitude, on Group (Bupropion, Nortriptyline, Placebo with Days (e.g., baseline, post-quit days 2, 5, 28) as the repeated measures factor. Three types of models will be evaluated. Model 1 will be restricted to startle responses to positive negative and cigarette stimuli and will include valence (positive/negative/cigarette) as a factor. This model will also include the corresponding value of the startle response to neutral stimuli as a covariate. In this way, we can compare the relative magnitude of startle responses to each valence adjusted for the response to neutral cues. The main effect of treatment Group is of primary interest in this model and will be evaluated first, followed by Days, and the Group X Day interaction. Other interactions including Group X Valence and Group X Valence X Days will also be explored. To assess Group differences (if any) at the beginning of the study, an a priori contrast on the baseline values only will also be carried out for this model, evaluating the main effect of Group and the Group by Valence interaction. In Model 2, startle will not be restricted to positive, negative or cigarette valences but will include all valences. The main effect of Group will be evaluated first, followed by Days, each of the two way interaction terms, and the Group X Day X Valence interaction. An a priori contrast will also be carried out as in Model 1 on the baseline values, to assess Group differences (if any) at the beginning of the study. The third model will involve only the post-quit assessments. This model is similar to Model 2, but will include the corresponding baseline value for each stimulus valence as a covariate. In this way, post cessation startle values may be expressed as a function of the corresponding pre cessation baseline values. As described in our preliminary studies, we believe this analysis can be quite informative, as it focuses on post cessation startle in relation to responses under nondeprived (baseline) conditions.
2. The emotional reactivity of smokers during cessation will be moderated by genotype. Our initial hypotheses focuses on the DRD2:
  - 2.1. We hypothesize that emotional reactivity will be lower for those carrying the DRD2 A1 and using bupropion vs. A1 smokers using either nortriptyline or placebo. A1 nortriptyline users are expected to

have lower reactivity than A1 placebo users[PCP18]. Homozygous A2s are expected to respond similarly to both drugs with higher levels of emotional reactivity being observed for placebo vs. either bupropion or nortriptyline.

This hypothesis will be evaluated using models similar to those described for hypothesis 1, but with the addition of Genotype (A1/A2 or A1/A1 vs. A2/A2) as a term in each model. We will specifically evaluate the main effect of Genotype first, followed by the Genotype X Group interaction (the term of interest). Other interactions involving Genotype with Days and Valence will be explored as described for Models 2 and 3 above. Planned contrasts involving the difference in startle magnitude between each Group condition, within Genotype, will also be carried out.

3. Higher levels of emotional reactivity of smokers at baseline and or during cessation will be inversely related to abstinence at the 3 and 6 month follow-ups.

- 3.1. Two types of analysis will be carried out. Our primary focus will be on predicting days to relapse. For this analysis, startle responses will serve as the independent variable with days to relapse as the dependent measure. The primary analysis will focus on the average startle response from the baseline assessment. In secondary models, average response to each valence will be included as predictors to determine the relative predictive strength of the different valences. Startle response from each of the post-quit assessments will also be examined as time dependent variables to determine if startle responses from the other assessments predicts relapse. Each model will also be evaluated controlling for or not controlling for treatment Group. For this analysis we will use Cox proportional hazards regression. We are also interested in predicting abstinence (yes/no) at the 3 and 6 month follow-up. Therefore we will also use the GLIMMIX Macro from SAS, which is an adaptation of the PROC Mixed procedure for hypothesis 1 and 2 for dichotomous out come variables (abstinence) to test whether startle responses are related to abstinence, modeling baseline, valence and time dependent characteristics of the model in the manner proposed above. Interactions between genotype (DRD2 A1 vs. A2) and startle in the prediction of abstinence, will also be explored using in the separate and combined valence models.

Covariates will be included in all models described above to correct for any baseline differences and help improve power. The covariates to be used include ethnicity, age, gender, smoking history, and depression history. Interactions between ethnicity or gender and genotype will be explored. If we find statistically significant interactions, separate models for each ethnicity or gender will also be tested.

The contribution of the WSWS, CES-D, PANAS scores and in-session ratings of craving and mood, to the observed startle effects in the primary hypotheses will be explored by fitting these variables as covariates in the above models. In addition we will examine the relationship between these measures, startle values for each valence, and with in sessions affect ratings using correlational procedures. Changes in these measures over time will also be evaluated using the same Mixed Model approach described above with Group and Genotype serving as between groups factors and Days as the repeated measure. Finally, the primary analyses of the startle magnitude described above will be repeated on the changes in skin conductance response and heart rate to determine the pattern of autonomic arousal displayed for baseline and withdrawal conditions.

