## A. Specific Aims

The specific aims of this proposal are to evaluate the differences in emotional reactivity (peak startle response to affective stimuli) during a cessation attempt among smokers treated with bupropion, nortriptyline or placebo and to determine if these differences are moderated by genotype. We will also assess the relationship between emotional reactivity and days to relapse, following the quit date.

This proposal will evaluate the following hypotheses:

1. The emotional reactivity of smokers during quitting will be significantly higher among those that receive placebo vs. either bupropion or nortriptyline therapy for smoking cessation. Emotional reactivity will be assessed by measuring the peak eye blink (EMG) response to an acoustic startle probe delivered during the presentation of emotionally valent stimuli (positive, negative, neutral, smoking related pictures).
2. The emotional reactivity of smokers during cessation will be moderated by genotype. Our initial hypothesis will focus on the DRD2:
  - 2.1. We hypothesize that emotional reactivity will be lower for those carrying the DRD2 A1 allele and using bupropion vs. A1 smokers using either nortriptyline or placebo. A1 nortriptyline users are expected to have lower reactivity than A1 placebo users[PCP1]. Homozygous A2s are expected to respond similarly to both drugs with higher levels of emotional reactivity being observed for placebo vs. either bupropion or nortriptyline.
3. Higher levels of emotional reactivity of smokers at baseline and during cessation will be inversely related to abstinence at the 3 and 6-month follow-up periods.

Although our initial genetic hypotheses are focused on the DRD2, we will also use emotional reactivity assessments to characterize the phenotypes of several other biomarkers that have potential importance for neuroregulatory function and response to pharmacotherapy for smoking cessation. These include the DRD4, SERT (serotonin transporter), DAT (dopamine transporter) and NET (norepinephrine transporter). Several exploratory hypotheses are proposed, for example:

1. We hypothesize that those carrying the long form of the DRD4 (6 repeat or longer) will experience less reactivity during either drug therapy than those homozygous for the short form.

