## Statistical Approach

**Table 3 Estimated Genotype & Allele Frequency**

Genotypes	Allele	Controls Freq. (%)	Smokers Freq. (%)
DRD2A	A1A1 or A1A2	25.9 a	42.6 g
DRD2B	A2A2	74.1	57.4
	B1B1 or B1B2	13.2 b	41.6 g
DRD4	B2B2	86.8	58.4
	SS	79 c	76 i
DAT	SL or LL	21	24
	9/9 or 9/10	55.8 d	46.7 d
SERT	10/10	44.2	53.3
	SS or SL	70.3 e	59.6 g
NET 1287G/A	LL	29.7	40.4
	GG	44 f	unknown
	GA	44	
	AA	12	

a= b= c= d= e= f= g= i=

Our primary analytic strategy involves the use a mixed model approach to examine the effects of the dependent variables (e.g., startle magnitude, time to rela9pse) across assessments. The mixed model approach provides a generalization to the classic linear regression model, using likelihood functions instead of least squares to estimate effects. The mixed model approach is ideally suited for analysis of repeated measures data in that it allows for more specific estimation of the correlation structure of the residuals, and more efficiently handles unbalanced designs and missing data, without excluding participants or imputing values. Fit statistics (e.g., Akaike's Information Criterion) will be evaluated for all models to ascertain the best fit of the correlation structure of the dataset. We use a computer program, PROC MIXED, (SAS Institute Inc, Cary, NC) to estimate and test the models. This procedure was used in our preliminary studies.

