## Power

Analysis of the startle responses will be conducted using mixed model regression. The study design involves both between subject and within subject fixed effects and correlations due to repeated measures on the participants. Within subject fixed effects include Days (baseline, post quit days 2,5, 28) and slide valence (positive, negative, neutral, cigarette). Between subjects effects include Treatment (Placebo, Bupropion, Nortriptyline) and Genotype (e.g., A1/A1 or A1/A2 and A2/A2 for our main hypothesis, and others as described for secondary hypotheses). Because of the nonstandard design, power calculations were conducted using simulations in SAS (PROC MIXED). To simplify calculations, we

**Table 4 Effect Sizes & Corresponding Differences in Startle Magnitude (µVolts) For Comparisons Genotype Main Effects Varying Prevalence Rates of the At Risk Allele**

Prevalence of "at risk" allele	Model 1	Model 2	Model 3
.5	.15 (3)	.29 (20)	.29 (16)
.4	.16 (3)	.30 (20)	.30 (16)
.3	.17 (4)	.32 (22)	.31 (17)
.2	.20 (4)	.36 (25)	.35 (19)

assume that the response to the slides at each level of valence within session will be averaged. The repeated measures on each subject are associated with correlations between observations from the same subject across sessions, and between observations from the same subject within session. We estimated these correlations using data from our previous work. For the primary hypothesis described below, we will fit three models. The first (Model 1) will restrict analyses to positive, negative and cigarette, stimuli and use the score to the neutral stimuli as a covariate, the second (Model 2) will use data from all valences together, and the third (Model 3) will use all data but examine post-quit scores controlling for baseline scores. The within subject-between-session and within subject-within session correlations varied for each model in our preliminary work. For Model 1, we estimated the within subject-between session and within subject-within session correlations to be .03 and .45, respectively; for the Model 2 we estimated them to be .7 and .9, respectively, and for Model3, we estimated them to be .6 and .9, respectively.

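### Hypothesis 1 is tested in three models that measure different Group effects, none is named as deciding, and Hypothesis 2's Genotype × Group term inherits the gap

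*Combined protocol and SAP*

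**What the plan says.** In the Power section: "For the primary hypothesis described below, we will fit three models". Primary Hypotheses, item 1.1, repeats this ("Three types of models will be evaluated") and defines them:

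- Model 1: positive, negative and cigarette responses with the neutral response as covariate; Days include baseline.
- Model 2: all four valences, no neutral covariate; Days include baseline.
- Model 3: post-quit sessions only, with the matching baseline value as covariate.

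Item 2.1 adds Genotype to each model and names Genotype × Group as the term of interest, but no model. The only alpha is the 0.05 used as a power input, and "Power calculations were repeated for each of the three models".

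H1 is stated twice. Specific Aims describes a probe "delivered during the presentation of emotionally valent stimuli (positive, negative, neutral, smoking related pictures"), and the Design Summary likewise makes neutral one of four valence levels. Primary Hypotheses speaks of "evaluating responses to emotionally valent stimuli (positive, negative, cigarette) relative to neutral visual slides". Both statements concern the quitting or withdrawal period.

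On the test itself, item 1.1 evaluates the overall Group effect first, while the Power section says: "For Hypothesis 1, we estimated power for the group contrast between placebo and either bupropion or nortriptyline". Neither says outright whether both drugs must differ from placebo, although that is the more natural reading.

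For Hypothesis 3, item 3.1 does name a primary analysis: the average startle response at baseline.

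**The concern.** All three models use peak startle, but their Group main effects are different quantities. Model 1 removes any shift that the neutral slides share. Models 1 and 2 average in a session held before any drug was taken, so a post-quit effect is diluted by a quarter. Model 3 leaves that session out of the outcome. One true drug effect can therefore be large in one model and negligible in another.

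Without a stated rule, two things follow. When the models disagree, the one to believe can be picked after the results are known. And the type I error rate of an H1 or H2 claim is undefined, because it depends on a decision rule that the plan does not give.

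**Working it through.** **Inputs from the plan (Power section).** N = 354, alpha 0.05, 80% power; detectable differences .17, .32 and .30 SD, or 4, 22 and 16 µV, for Models 1, 2 and 3. Between-session and within-session correlations: .03 and .45 (Model 1), .7 and .9 (Model 2), .6 and .9 (Model 3).

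**Assumed here.** 118 per arm (1:1:1), two-sided tests, no dropout.

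**1. The plan's own figures.** With v valences and d sessions, the variance of a subject mean in SD² units is [1 + (v−1)r_within + (d−1)v·r_between]/(vd), and the detectable effect is 2.802·√(2·variance/118).

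- Model 1 (v=3, d=4): variance .181, effect .155 (plan .17)
- Model 2 (v=4, d=4): variance .756, effect .317 (plan .32)
- Model 3 (v=4, d=3): variance .708, effect .307 (plan .30)

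Models 2 and 3 reproduce. Model 1 is stated more conservatively than this formula gives. The plan used simulations whose settings are not all reported, so this is not called an error, and nothing below depends on it.

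**2. Size of the Group main effect in each model.** Post-quit sessions are 3 of 4; emotional and cigarette slides are 3 of 4 valences. The neutral slope is .90 (from the within-session correlation) to .94 (from SDs 4/.17 = 23.5 and 22/.32 = 69: √(1 − (23.5/69)²) = .94).

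- Both drugs −22 µV on all slides, post-quit. Model 1: 22 × ¾ × (1 − .90 to .94) = 1.65 to 0.99. Model 2: 22 × ¾ = 16.5. Model 3: 22.
- Both drugs −16 µV on emotional and cigarette slides only, post-quit. Model 1: 16 × ¾ = 12. Model 2: 16 × ¾ × ¾ = 9. Model 3: 16 × ¾ = 12.

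**3. Chance that the Group test is significant.** At the plan's own precision, SE = detectable difference/2.80; the 2-df test has noncentrality 4d²/(3·SE²), where d is the effect from step 2. Example, Model 2, first case: SE = 22/2.80 = 7.86, noncentrality = 4 × 16.5²/(3 × 7.86²) = 5.9, power 58%.

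| True effect | Model 1 | Model 2 | Model 3 |
|---|---|---|---|
| 22 µV, all slides: plan precision | 10–20% | 58% | 98% |
| 22 µV, all slides: simulated | 16–18% | 58% | 99% |
| 16 µV, emotional and cigarette: plan precision | 100% | 20% | 58% |
| 16 µV, emotional and cigarette: simulated | 100% | 20% | 60% |

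The simulations use SD 69 µV, correlation .9 within session, .76 between post-quit sessions and .64 from baseline to post-quit (average .70). This split is an assumption; the plan gives only .7. It yields Model 1 correlations of .47 and .04 (for the first of these the plan says: "For Model 1, we estimated the within subject-between session and within subject-within session correlations to be .03 and .45, respectively") and detectable differences of 4.9, 21.9 and 15.5 µV (plan 4, 22, 16).

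**4. False-positive rate if any one of the three models may decide.** 40,000 null trials; correlations between the models' test statistics came out at .52, .28 and .53. The documents do not give these, so brackets show .95 down to 0.

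| Reading of H1 | One model | Any of three |
|---|---|---|
| Group test, then placebo higher | 2.0% | 5.3% [3.2–6.1%] |
| Both drugs below placebo, neither works | 0.4% | 1.2% [0.8–1.4%] |
| Both drugs below placebo, only one works | up to 2.5% | up to 6.4% [3.7–7.3%] |
| Placebo above at least one drug | 4.6% | 11.2% [6.6–13.0%] |
| Overall Group test, no direction | 5.0% | 12.9% [7.5–14.2%] |

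For H2's Genotype × Group term (.426 × 118 ≈ 50 A1 carriers per arm) the rates are 5.0% and 13.0%; no range was computed.

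**The case against.** **The text leans to Model 1.** The analysis-section wording of H1 measures responses against neutral slides and directly precedes Model 1, only Model 1's description calls the Group effect of primary interest, and neutral adjustment was used in the preliminary work. The lean is real, but it does not name a deciding model. The remark ranks terms inside Model 1, and Model 2 also evaluates Group first. Specific Aims and the Design Summary treat neutral as one of four stimulus types. The hypothesis concerns withdrawal, and Model 1's Group effect includes a session before it.

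**Fit statistics could choose.** They are to be used "to ascertain the best fit of the correlation structure of the dataset". That selects a covariance, not one of three models with different data and covariates.

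**The preliminary results were similar with and without baseline adjustment.** That was one interaction in a small interim sample (genotype on 62 participants), and it supplies no rule.

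**Model 2's interactions would catch what its main effect misses.** Often true: Group × Day has about 89% power in the first case (nearer 99% with a flat .7 between-session correlation), and Group × Valence about 100% in the second. The discordance shown is therefore about the Group main effect, which is the term evaluated first.

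**The inflation is overstated.** A reader might infer that H1 carries a 13% false-positive rate. The documents do not support that. H1 is directional, the 13% belongs to a non-directional test, and the plan never says that one significant model suffices.

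**Conclusion.** The point stands: H1 and H2 each have three candidate answers and no stated way to choose. Discordance is the main problem, because the model most likely to be significant changes with the form of the drug effect, at effect sizes the plan itself powers for. The error-rate problem is conditional on an any-model rule and on how H1 is read. Where both drugs must be below placebo the excess is small (1.2% against 0.4%, at most 6.4% against 2.5%); where one drug suffices it is larger (11.2% against 4.6%). The plan-precision figures rest on the plan's detectable differences, equal allocation and a two-sided test; the simulated figures also rest on the assumed covariance and no dropout. It would go too far to conclude that the plan intends to claim success from whichever model is significant, or that any of the three is invalid.

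**What to change.** Before unblinding:

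1. Name one deciding model and one deciding test (overall Group test or placebo contrasts) for H1, and one deciding model for H2's Genotype × Group term. Label the other models supportive. Justify the choice on both the role of neutral slides and the post-quit window, and align Specific Aims, Design Summary and Primary Hypotheses with it. If all three models stay deciding, apply Holm or Hochberg across them at family-wise 0.05, with any drug contrasts in the same family; Dunnett within each model alone would leave 13.1% if any model counts.
2. State whether H1 needs both drugs or at least one below placebo. If one suffices, use Dunnett or Hochberg for the two contrasts in the deciding model. If both are required, no adjustment is needed there.
3. Restate power for the chosen rule.

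The cost is plan wording and somewhat lower stated power at the plan's effects:

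- Dunnett (critical value 2.21): Φ(2.802 − 2.212) = 72% per contrast. The detectable difference rises by (2.212 + 0.842)/2.802 = 1.09, to 4.4, 24.0 and 17.4 µV.
- Both drugs required: about 69% (bivariate normal, correlation .5); 80% needs a difference about 12% larger.
- Holm across three models, first step (2.39): Φ(2.802 − 2.394) = 66%. The detectable difference rises by up to 15%, to 4.6, 25.4 and 18.5 µV.

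H1 or H2 could no longer be claimed from a supportive model. All three can still be reported, and H2's planned within-genotype contrasts can stay as written.
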